3.3. Patient Instructions

Patients must be instructed not to take any medications, including over-the-counter products, without first consulting with the investigator.

Patients will be offered medications to manage anxiety and pain due to the EP procedure by the investigator (see Section 4.4.3).

3.3.1. Concomitant Medications

3.3.1.1. Allowed

Concomitant medications which are allowed while participating on this trial are listed in **Table 1**.

Table 1. Supportive Medications

Supportive medication/class of drug:	Usage:
Concomitant medications or treatments (e.g. acetaminophen or diphenhydramine) deemed necessary to provide adequate prophylactic or supportive care, except for those medications identified as "prohibited," as listed above	To be administered as prescribed by the Investigator

Version Number: 1.8 Date: July 26, 2019

Proprietary of MD Anderson Cancer Center

Best supportive care (including antibiotics, nutritional support, correction of metabolic disorders, optimal symptom control, and pain management [including palliative radiotherapy to non-target lesions, etc.])	Should be used, when necessary, for all subjects
Inactivated viruses, such as those in the influenza vaccine	Permitted
Highly active antiretroviral therapy (HAART)	Patient remains stable on current HAART (Highly active antiretroviral therapy) while on study. Viral load<75 copies/mL. CD4 counts ≥ 200 criteria at all times. Obtain routine outpatient ID consult for management of HIV prior to commencing study.

3.3.1.2. Prohibited

The following medications are considered exclusionary during the study, and exceptions to the exclusion are included. The MDACC IND Office must be notified if a patient receives any of these during the study.

- 1. Any concurrent chemotherapy, radiotherapy, immunotherapy, IP, biologic, or hormonal therapy for cancer treatment. Concurrent use of hormones for non-cancer-related conditions (e.g., insulin for diabetes and hormone replacement therapy) is acceptable. Local treatment of isolated lesions, excluding target lesions, for palliative intent is acceptable (e.g., by local surgery or radiotherapy).
- 2. Immunosuppressive medications including, but not limited to, systemic corticosteroids at doses exceeding 10 mg/day of prednisone or equivalent, methotrexate, azathioprine, and tumor necrosis factor-alpha (TNF-α) blockers. Use of immunosuppressive medications for the management of IP-related AEs, or in subjects with contrast allergies is acceptable). In addition, use of inhaled, topical, and intranasal corticosteroids is permitted. A temporary period of steroids will be allowed for different indications after discussion with the medical monitor (e.g., chronic obstructive pulmonary disease, radiation, nausea, etc.).
- 3. Use of anticoagulants and irreversible platelet inhibitors (e.g. clopidogrel, prasugrel, ticagrelor etc.) are not allowed. Low dose aspirin for cardiac prophylaxis is allowed.
- 4. Drugs with laxative properties and herbal or natural remedies for constipation should be used with caution through 90 days after the last dose of durvalumab during the study.
- 5. Sunitinib should not be given concomitantly or through 90 days after the last dose of durvalumab (acute renal failure has been reported with combination therapy of durvalumab and sunitinib).
- 6. Live attenuated vaccines should not be given through 30 days after the last dose of IP (including SoC)

Version Number: 1.8 Date: July 26, 2019

Proprietary of MD Anderson Cancer Center

3.3.2. Contraception

Female subjects of childbearing potential who are sexually active with a non-sterilized male partner must use at least one highly effective methods of effective contraception (**Table 2**) from the time of screening and must agree to continue using such precautions for 90 days after the last dose of IP. Cessation of birth control after this point should be discussed with a responsible physician.

Females subjects of childbearing potential are defined as those who are not surgically sterile (i.e., bilateral tubal ligation, bilateral oophorectomy, or complete hysterectomy) or postmenopausal. Women will be considered post-menopausal if they have been amenorrheic for 12 months without an alternative medical cause. The following age-specific requirements apply:

- Women > 50 years of age would be considered post-menopausal if they have been amenorrheic for 12 months or more following cessation of exogenous hormonal treatments and if they have luteinizing hormone and follicle-stimulating hormone levels in the post-menopausal range for the institution or underwent surgical sterilization (bilateral oophorectomy or hysterectomy).
- Women ≤ 50 years of age would be considered post-menopausal if they have been amenorrheic for 12 months or more following cessation of all exogenous hormonal treatments, had radiation-induced menopause with last menses >6 months ago, had chemotherapy-induced menopause with last menses >1 year ago, or underwent surgical sterilization (bilateral oophorectomy, bilateral salpingectomy or hysterectomy).

A highly effective method of contraception is defined as one that results in a low failure rate (i.e., less than 1% per year) when used consistently and correctly. Highly effective methods of contraception are presented in **Table 2**.

Version Number: 1.8 Date: July 26, 2019

Proprietary of MD Anderson Cancer Center

Table 2. Effective Methods of Contraception

Barrier Methods ^{a,b}	Intrauterine Methods	Hormonal Methods
Male condom plus spermicide	e.g., Copper T intrauterine device ^d	e.g., Implants ^d
Cap plus spermicide		Hormone shot or injection ^d
Diaphragm plus spermicide	Progesterone T intrauterine device ^c	Combined pill ^d
	Levonorgesterel-releasing	Minipilla
	intrauterine system (e.g., Mirena® ^{c,d}	Patch ^d

- a. Not highly effective (failure rate of = 1% per year)
- b. A male condom plus cap, diaphragm, or sponge with spermicide (double barrier methods) are also considered acceptable, but not highly effective, birth control methods
- c. Also considered a hormonal method
- d. Highly effective (failure rate of < 1% per year)

Non-sterilized male patients who are sexually active with a female partner of childbearing potential must use a condom with spermicide from screening to 90 days after the final dose of IP.

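### Section 3.3.2 requires LH/FSH confirmation of menopause only above age 50; at 50 or under no route needs a hormone result, and radiation-induced menopause qualifies once last menses was more than 6 months ago

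*Combined protocol and SAP*

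**What the plan says.** Section 3.3.2 first gives a general rule: "Women will be considered post-menopausal if they have been amenorrheic for 12 months without an alternative medical cause". It then splits by age.

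- **Over 50.** Twelve months' amenorrhea after stopping exogenous hormones is required, and the woman qualifies only "if they have luteinizing hormone and follicle-stimulating hormone levels in the post-menopausal range for the institution". Surgical sterilization is the alternative.
- **50 or under.** The bullet begins "Women ≤ 50 years of age would be considered post-menopausal if they have been amenorrheic for 12 months or more following cessation" of all exogenous hormones. It then offers alternatives: "had radiation-induced menopause with last menses >6 months ago", "had chemotherapy-induced menopause with last menses >1 year ago", or surgery ("bilateral oophorectomy, bilateral salpingectomy or hysterectomy"). LH and FSH are not mentioned.

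The only other reference to these hormones is Table 3 footnote w. It adds LH and FSH to the screening pregnancy test for women of childbearing potential who may be post-menopausal, and states no required range.

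The classification controls two things. Section 3.3.2 imposes contraception only on women of childbearing potential. Section 6.5.3 and Table 3 footnote v require pregnancy tests only of the same group, and section 6.5.3 asks for a negative serum result before each administration of study product.

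**The concern.** The laboratory check applies to the older group and is absent for the younger group, who are more likely to be fertile. The text gives no criterion for deciding that menopause was induced by radiation or chemotherapy, so on those two routes a clinical judgment stands without a hormone result behind it.

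One label switches off both prevention and detection. If a woman of 50 or under is wrongly classed as post-menopausal, is fertile and is exposed to pregnancy, the pregnancy could go unnoticed while dosing continues, although section 7.6.2 requires both products to stop at once. Exclusion criterion 19, section 3.4 and section 7.6.2 act on a known pregnancy; none of them detects one.

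The case is foreseeable here. Entry is open from age 18, one cohort is cervical cancer, the first three places are limited to cervical, vulvar or vaginal cancer, and inclusion criterion 4 describes disease that has failed standard therapy or cannot be cured by salvage such as re-irradiation.

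**Working it through.** The plan states no figure to reproduce. The main check is a comparison of the routes in section 3.3.2.

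| Non-surgical route | Time condition | LH/FSH result required? |
|---|---|---|
| General sentence | 12 months' amenorrhea, no other medical cause | No |
| Over 50 | At least 12 months off hormones | Yes, in post-menopausal range |
| 50 or under, plain amenorrhea | At least 12 months off all hormones | No |
| 50 or under, radiation-induced | Last menses more than 6 months ago | No |
| 50 or under, chemotherapy-induced | Last menses more than 1 year ago | No |

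Only the radiation route is shorter than the general 12 months; the difference is 12 − 6 = 6 months.

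**Does footnote w close the gap?** It covers women still classed as of childbearing potential. A woman who already meets the 50-or-under bullet has left that class, so the footnote does not clearly reach her. If LH and FSH are drawn anyway, no rule at or below 50 says what a result outside the range would change.

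**How much exposure does the shorter radiation route add, per woman?** Assumptions: 6 months = 365/2 = 182.5 days; the woman is just past 6 months at screening, which is the extreme case; visits fall on nominal dates; and treatment runs without interruption.

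- Screening is Day −28 to −1, so she reaches 12 months between 182.5 − 28 = 154.5 and 182.5 − 1 = 181.5 days after Day 1.
- The visit in week w falls (w − 1) × 7 days after Day 1: Week 20 = 133, Week 24 = 161, Week 28 = 189.
- From section 4.4.1, MEDI0457 is given at Weeks 1, 3, 7, 12, 20 and 28, and durvalumab at Weeks 4, 8, 12, 16, 20, 24 and 28.
- Distinct dosing visits before 154.5 days: Weeks 1, 3, 4, 7, 8, 12, 16, 20 = 8. Before 181.5 days, Week 24 is added = 9. Week 24 counts if 182.5 − d > 161, that is, if screening is fewer than 21.5 days before Day 1.

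Pregnancy tests forgone in that window depend on which rule is counted:

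- Section 6.5.3 (screening plus one before each dose): 1 + 8 = 9 to 1 + 9 = 10.
- Table 3 (screening plus Weeks 1, 4, 8, 12, 16, 20, and Week 24 as a repeat of Cycle 4): 7 to 8. Table 3 shows no test at Weeks 3 and 7, which accounts for the difference of 2.

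Where a negative serum test falls within 3 days before Day 1, footnote x drops the Week 1 test and the count is one lower. These counts describe only the extra 6 months on the radiation route. On every younger route the hormone check is absent for as long as treatment lasts.

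**The case against.** The strongest reply has four parts.

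**Partial safeguards exist.** Footnote w has no age limit and treats a woman of uncertain status as of childbearing potential, so an investigator may well have hormone values when classifying her. The radiation route is also more than a 6-month clock, because menopause must be judged present and radiation-induced. This stands in part. It makes misclassification less likely, but it leaves the result without force at or below 50.

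**It is a clinical choice.** The documents cite no standard that the younger bullet breaches. The plain 12-month route matches the general rule, and the chemotherapy route is no shorter. That is fair. The point is an unexplained asymmetry in a safeguard, not a breach.

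**Harm needs several things together:** misclassification, retained fertility and exposure to pregnancy. This stands, and it limits the weight of the point.

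**The visit counts are an extreme case.** They assume entry just past 6 months and treatment to Week 20 or 24 without progression or toxicity. This also stands; they are an upper illustration, not an estimate.

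Three stronger readings are tempting and not supported. A reader might infer that any non-sterile woman of 50 or under qualifies at 6 months; the text confines that interval to radiation-induced menopause. A reader might infer that the two age labels were swapped; the pattern would fit, but nothing in the documents confirms it, and the over-50 bullet could equally be the unusually strict one. A reader might infer that the section contradicts itself; the radiation and chemotherapy routes read naturally as stated exceptions to the general rule.

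**Conclusion.** The concern holds as a participant-safety wording point. LH and FSH in the post-menopausal range are a condition only for non-sterilized women over 50. Non-sterilized women of 50 or under need no hormone result on any of three routes, one of which opens at more than 6 months since last menses, and footnote w does not supply the missing condition.

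The number of women affected cannot be derived. For one misclassified woman entering just past 6 months on the radiation route, the shorter interval alone spans 8 to 9 dosing visits, under the assumptions set out above. No endpoint, analysis set or stopping rule is affected. The case for amending rests on a low-probability but serious outcome and a cheap remedy, and it does not depend on knowing why the bullets differ.

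**What to change.** Leave the over-50 bullet, all surgical routes and the existing time limits unchanged. The surgical routes include those in the general definition ("bilateral tubal ligation, bilateral oophorectomy, or complete hysterectomy").

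Add to the 50-or-under bullet: each non-surgical route (12 months' amenorrhea, radiation-induced, chemotherapy-induced) also requires LH and FSH in the institution's post-menopausal range; until this is confirmed, the woman follows the childbearing-potential rules for contraception and pregnancy testing.

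Reword Table 3 footnote w: LH and FSH are drawn at screening for any woman who is not surgically sterile and may be post-menopausal, including women of 50 or under, and may be repeated at a later scheduled blood draw if not confirmed at screening.

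Lengthening the radiation route to 12 months is optional and is not needed once the hormone condition applies. Doing both would make the treatment-induced routes nearly redundant with the plain 12-month route.

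The cost is a wording amendment and a few more hormone and pregnancy tests; LH/FSH is already in Table 3 at screening. The main downside falls on women of 50 or under with treatment-induced menopause who take hormone replacement, which section 3.3.1.2 permits: "Concurrent use of hormones for non-cancer-related conditions (e.g., insulin for diabetes and hormone replacement therapy) is acceptable". Those who cannot be confirmed would keep contraception and pregnancy testing.

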3.3.3. Blood donation

Subjects should not donate blood while participating in this study until 90 days after the last dose of IP.

3.4. Discontinuation of Investigational Product

An individual patient will not receive any further IP if any of the following occur.

- Initiation of subsequent anticancer therapy including another investigational agent.
- Confirmed PD: the initial assessment of PD by RECIST v1.1 (baseline PD assessment) will be confirmed by a repeat evaluation at the next tumor assessment time point, but no sooner than 4 weeks later. If any tumor assessment time point (beyond the first PD assessment) shows ≥ 20% increase in the overall tumor burden (the sum of diameters of target lesions and new lesions), when compared to the baseline PD assessment (the sum of diameters of target lesions and new lesions), the patient would be deemed as having confirmed PD and must be discontinued.
- An AE that, in the opinion of the Investigator, supporting company, or the MDACC IND Office, contraindicates further dosing.
- Patient experienced a DLT as defined in Section 6.7.2.
- Withdrawal of consent from further treatment with IP or lost to follow-up.

Version Number: 1.8 Date: July 26, 2019

Proprietary of MD Anderson Cancer Center

- Patient is determined to have met one or more of the exclusion criteria or failed to meet all of the inclusion criteria for study participation and continuing to receive IP might constitute a safety risk.
- Pregnancy or intent to become pregnant.
- Non-compliance with the study protocol that, in the opinion of the Investigator, supporting company, or the MDACC IND Office, warrants withdrawal from treatment with IP (e.g., refusal to adhere to scheduled visits).
- The treating Physician determines it is not in the best interest of the patient to continue.

At any time, patients are free to discontinue IP or withdraw from the study (i.e., IP and assessments) without prejudice to further treatment. If a patient is withdrawn from study, see Section 3.5.2.

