1.6. Study Design

This study will be an open label, multi-cohort, phase II trial for the combination therapy of MEDI0457 (INO-3112) and Durvalumab (MEDI4736) in patients with HPV-16 and/or -18 related malignancies. This study will enroll 3 cohorts of patients with HPV-16/18 (+) tumors. The three cohorts are:

- 1. HPV-16/18 cervical cancer,
- 2. HPV-16/18 rare tumors (anal, penile, vulvar, vaginal), and
- 3. HIV (+) HPV-16/18 malignancies (any site).

Each cohort will have a two-stage design with predetermined stopping rules based on ORR after stage I and each cohort will function independently clinically. After each cohort completes accrual to stage I, only the two cohorts with the most responses will move on to stage 2.

Therefore, accrual to stage 2 will not start till all three cohorts have completed stage I. However, if a single cohort has a high response rate (≥4 responses out of 9 patients), the second stage of accrual may proceed prior to other cohorts completing stage I.

At the onset of the study, only patients with cervical, vulvar, or vaginal cancers will be enrolled for the first 3 slots. Once all 3 of these patients have completed the first 6 weeks of treatment, enrollment will be opened to all included cancer histotypes.

Both MEDI0457 and durvalumab treatment will continue until confirmed disease progression or unacceptable toxicity. Either treatment may be stopped by the investigator if a SAE is deemed to be related to that treatment while the other treatment continues.

The target population consists of male or female patients 18 years of age or older with recurrent or metastatic HPV 16- or 18-associated cancers with persistent or progressive disease (PD) after initial standard-of-care treatment and lacking a curative treatment option.

Eligible patients must have at least one "measurable target lesion"—according to RECIST version 1.1—that has not been previously irradiated. In addition, if the primary lesion is not large enough for a biopsy without changing radiologic findings for following response, one additional lesion

Version Number: 1.8 Date: July 26, 2019

Proprietary of MD Anderson Cancer Center

that can be safely biopsied at screening and prior to the first dose of MEDI0457 at Week 1 will be required.

All patients will receive combination treatment with MEDI0457 and durvalumab as per the **Planned Dosing Schedule (Section 4.4.1, Figure 1**, and **Table 3**).

[figure not shown]

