Patients who discontinued from treatment for reasons other than PD will continue disease assessments until confirmed PD or start of subsequent anticancer therapy.

The response to immunotherapy may differ from the typical responses observed with cytotoxic chemotherapy including the following:

- Response to immunotherapy may be delayed,
- Response to immunotherapy may occur after PD by conventional criteria,
- The appearance of new lesions may not represent PD with immunotherapy, and/or
- SD while on immunotherapy may be durable and represent clinical benefit.

Based on the above-described unique response to immunotherapy and based on guidelines from regulatory agencies, e.g., European Medicines Agency's "Guideline on the evaluation of anticancer medicinal products in man" (EMA/CHMP/205/95/Rev.4) for immune modulating anticancer compounds, this study will include the following in addition to standard RECIST 1.1 criteria:

- RECIST will be modified so that PD must be confirmed with a second radiologic assessment, preferably, 5 weeks (+/- 7 days) after the initial assessment of PD in the absence of clinically significant deterioration. Treatment with study regimen should continue between the initial assessment of progression and confirmation for progression at outlined in Tables 4.
- In addition, subjects may continue to receive the study regimen beyond confirmed PD in the absence of clinically significant deterioration and if investigators consider that subjects may be deriving benefit from treatment and there are no more suitable alternative treatments available for the subject.

Version Number: 1.8

Proprietary of MD Anderson Cancer Center Date: July 26, 2019

Modification of RECIST as described is meant to discourage the early discontinuation of the study regimen and provide a more complete evaluation of its anti-tumor activity than would be seen with conventional response criteria. Nonetheless, the efficacy analysis will be conducted by programmatically deriving each efficacy endpoint based on the first evidence of progression (by modified RECIST 1.1 criteria described below) when progression is confirmed by a second scan.

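### Sections 3.4 and 6.3 contradict each other on treatment after confirmed progression and on what confirms it, and 6.3 and 8.3.2 disagree on whether a PFS or DCR progression must be confirmed

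*Combined protocol and SAP*

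**What the plan says.** **Treatment after confirmed PD.** Section 3.4 opens its list of stopping events with "An individual patient will not receive any further IP if any of the following occur". For confirmed PD it adds that "the patient would be deemed as having confirmed PD and must be discontinued". Section 1.6 agrees: "Both MEDI0457 and durvalumab treatment will continue until confirmed disease progression or unacceptable toxicity". Section 6.3 says that "subjects may continue to receive the study regimen beyond confirmed PD in the absence of clinically significant deterioration", provided the investigator thinks the patient may be benefiting and there is no more suitable alternative. Section 4.4.1 gives both drugs until progression or unacceptable toxicity and does not say confirmed. Neither 3.4 nor 6.3 refers to the other.

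**What confirms PD.** Under 3.4, a first PD "will be confirmed by a repeat evaluation at the next tumor assessment time point, but no sooner than 4 weeks later". The next sentence deems PD confirmed if a later assessment "shows ≥ 20% increase in the overall tumor burden" relative to the first PD scan, counting target and new lesions. Under 6.3, "PD must be confirmed with a second radiologic assessment, preferably, 5 weeks (+/- 7 days) after the initial assessment of PD", with no size threshold. Section 6.3 then points forward to modified RECIST 1.1 criteria, but none follow.

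**Endpoints.** Section 6.3 derives each efficacy endpoint by program from the first evidence of progression, provided a second scan confirms it. Section 8.3.2.2 runs PFS to objective progression or death and dates progression at the earliest RECIST 1.1 scan showing it. Section 8.3.2.3 counts stable disease as control only if there is no progression for 24 weeks. Neither mentions confirmation.

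**The concern.** Two questions are mixed together in the text, and each has more than one answer.

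The first is about conduct. A patient kept on drug after confirmed PD complies with 6.3 and violates 3.4. Sites can act differently in good faith, so exposure and the safety data gathered under it would differ by site. The term confirmed PD also controls follow-up. For patients who stop treatment for reasons other than progression, tumor assessments (6.3 and Table 3, footnote g) and capture of drug- or procedure-related SAEs (3.5 and 7.4.1) run until confirmed PD. An unclear definition therefore also changes what is collected.

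The second is about analysis. Whether a first PD must be confirmed decides whether some patients have a PFS event and whether they count towards DCR-24w. Section 6.3 and Section 8.3.2 answer this differently, so the analyst would have to choose after seeing the data.

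**Working it through.** The plan states no figure on this point. The check sets the passages side by side and applies arithmetic to their own windows and thresholds.

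**1. Treatment after confirmed PD.**
- 3.4: no further investigational product, no exception.
- 1.6: treat until confirmed progression (agrees with 3.4).
- 6.3: may continue, subject to conditions.
- 4.4.1: until progression, confirmation not mentioned.

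No reading satisfies both 3.4 and 6.3 for a patient who continues.

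**2. Timing of confirmation.**
- 6.3: 35 ± 7 days = 28 to 42 days = 4 to 6 weeks after first PD.
- 3.4, year 1 (scans every 8 weeks ± 3 days): 56 ± 3 = 53 to 59 days = 7.6 to 8.4 weeks.
- 3.4, afterwards (every 12 weeks ± 7 days): 84 ± 7 = 77 to 91 days = 11 to 13 weeks.

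The 3.4 figures take the first PD scan as a scheduled scan on its nominal date. They do not overlap with the preferred 6.3 window. An unscheduled first PD scan could bring the next time point closer, subject to the 4-week floor in 3.4.

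**3. Durvalumab doses while awaiting confirmation** (every 4 weeks, no delays).
- Confirmation at 4 to 6 weeks: 1 to 2 doses.
- Confirmation at 8 weeks: 2 doses.
- 12-week scan phase: no count given. Section 4.4.2 caps checkpoint-inhibitor doses at 13, and without delays the 13th falls at week 4 + 12 × 4 = week 52.

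The larger difference comes after confirmation: no doses under 3.4, continued dosing under 6.3.

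**4. Size criterion** (illustrative sums, no new lesions; smallest sum 50 mm).
- First PD: 50 × 1.20 = 60 mm.
- 3.4 growth test: 60 × 1.20 = 72 mm, which is 72/50 = 1.44, or +44% over the smallest sum.
- Second scan at 66 mm: 66/50 = 1.32, so it still shows PD; 66/60 = 1.10, so it misses the growth test.

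If the growth test is read as required, any second scan from 60 mm to below 72 mm is unconfirmed under 3.4 and confirmed on a plain reading of 6.3. If it is read as one sufficient route, this difference disappears.

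**5. Endpoint status.**

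| Course after first PD | 8.3.2.2 / 8.3.2.3 | 6.3 |
|---|---|---|
| Second scan confirms | Event, dated at first PD | Event, dated at first PD |
| Second scan does not confirm | Event at first PD | Not an event at first PD |
| No second scan | Event at first PD | Not an event at first PD, read literally |

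A patient in the second or third row whose first PD falls before week 24, without CR or PR by then, is a DCR failure under 8.3.2.3. Under 6.3 that first PD does not make the patient a failure. One reclassified patient moves DCR by 1/34 = 2.9 percentage points in a full cohort, or 1/9 = 11.1 points in a cohort that ends after stage 1.

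**The case against.** The strongest defence is that these are separate rules for separate purposes. Section 3.4 is a stopping rule, not an endpoint definition. Section 8.3.2 is the statistical text, says RECIST v1.1 throughout, and is applied by program, so sites do not choose the PFS or DCR rule. If 8.3.2 alone governs, the differences between 3.4 and 6.3 change neither endpoint. The confirmation wording is also softer than it looks. The 6.3 interval is only preferred, so a scan at 8 weeks breaches neither section. The first sentence of the 3.4 bullet can be read as confirmation by any repeat evaluation, with 20% growth as one sufficient route.

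Much of this stands, and it rules out three stronger readings that a reader might infer:
- **That the treatment contradiction moves PFS or DCR.** It does not. By the time PD is confirmed, the event is already dated at first PD under both 6.3 and 8.3.2.2.
- **That 3.4 definitely requires 72 mm in the example.** That is one possible reading of an ambiguous bullet.
- **That sites can alter PFS or DCR by picking a section.** The documents support this for exposure; endpoint derivation is central.

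The defence does not remove the conflict between 6.3 and 8.3.2. Section 6.3 states expressly how each efficacy endpoint is to be derived, and nothing says that 8.3.2 overrides it. Nor does it touch the contradiction over treatment.

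**Conclusion.** The text is wrong as written in three places: treatment after confirmed PD (3.4 and 1.6 against 6.3, with 4.4.1 silent on confirmation), what confirms PD (3.4 against 6.3), and whether a PFS or DCR progression needs confirmation (6.3 against 8.3.2.2 and 8.3.2.3). The first affects exposure and safety data. The second affects when treatment and follow-up end. The third affects event status for any patient whose first PD is never confirmed; where a second scan confirms, status and date agree.

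The size per patient is 2.9 points of DCR in a cohort of 34. The number of such patients cannot be computed from the documents. The millimetre example rests on assumed lesion sums and on one reading of 3.4.

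Because 6.3 speaks of every efficacy endpoint, a reader might infer that the two-stage ORR decision is at risk too. The documents do not show that. Sections 8.1.2 and 8.3.1 define ORR by RECIST 1.1 responses, and the conflicting passages concern progression. The consequence shown is limited to secondary endpoints, exposure and follow-up.

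**What to change.** 1. Reconcile 1.6, 3.4, 4.4.1 and 6.3 on treatment after confirmed PD and on what confirms PD: the interval, whether a growth threshold applies, and whether it is required or only sufficient. Which clinical rule to adopt is for the sponsor and investigators; this review takes no position.
2. Supply the modified RECIST 1.1 criteria that 6.3 announces, or delete the reference.
3. Make 6.3 and 8.3.2.2–8.3.2.3 agree on whether a progression must be confirmed to count for PFS and DCR-24w, by which criterion, and how a first PD with no second scan is handled. Report the other version as a sensitivity analysis.

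The endpoint rule need not be the same as the treatment-stopping rule, as long as each is stated once and labelled.

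Cost: protocol and analysis wording, plus one extra analysis.
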